14.1. Overview

This section defines the types of safety data that will be collected under this protocol and outlines the procedures for appropriately collecting, grading, recording, and reporting those data. Adverse events that are classified as serious according to the definition of health authorities must be reported promptly to the sponsor [DAIT/NIAID]. Appropriate notifications will also be made to site principal investigators, Institutional Review Boards (IRBs), and health authorities.

Information in this section complies with ICH Guideline E2A: Clinical Safety Data Management: Definitions and Standards for Expedited Reporting, ICH Guideline E-6: Guideline for Good Clinical Practice, 21CFR Parts 312 and 320, and applies the standards set forth in the National Cancer Institute (NCI), Common Terminology Criteria for Adverse Events (CTCAE), Version 4.0: <http://ctep.cancer.gov/reporting/ctc.html>.

14.2. Definitions

14.2.1. Adverse Event (AE)

Any untoward or unfavorable medical occurrence associated with the subject's participation in the research, whether or not considered related to the subject's participation in the research (modified from the definition of adverse events in the 1996 International Conference on Harmonization E-6 Guidelines for Good Clinical Practice) (from OHRP "Guidance on Reviewing and Reporting Unanticipated Problems Involving Risks to Subjects or Others and Adverse Events (1/15/07)" <http://www.hhs.gov/ohrp/policy/advevntguid.html#Q2>)

14.2.1.1. Suspected Adverse Reaction (SAR)

Any adverse event for which there is a reasonable possibility that the investigational drug [or investigational study therapy regimen] caused the adverse event. For the purposes of safety reporting, 'reasonable possibility' means there is evidence to suggest a causal relationship between the drug and the adverse event. A suspected adverse reaction implies a lesser degree of certainty about causality than adverse reaction, which means any adverse event caused by a drug (21 CFR 312.32(a)).

14.2.2. Unexpected Adverse Event

An adverse event or suspected adverse reaction is considered "unexpected" if it is not listed in the Investigator Brochure or package insert or is not listed at the specificity, severity or rate of occurrence that has been observed.

"Unexpected" also refers to adverse events or suspected adverse reactions that are mentioned in the Investigator Brochure or package insert as occurring with a class of drugs or as anticipated from the pharmacological properties of the drug, but are not specifically mentioned as occurring with the particular drug under investigation (21 CFR 312.32(a))

14.2.3. Serious Adverse Event (SAE)

An adverse event or suspected adverse reaction is considered "serious" if, in the view of either the investigator or Sponsor, it results in any of the following outcomes (21 CFR 312.32(a)):

1. Death.
2. A life-threatening event: An AE or SAR is considered "life-threatening" if, in the view of either the investigator or Sponsor [add DAIT/NIAID or other Sponsor, *if applicable*], its occurrence places the subject at immediate risk of death. It does not include an AE or SAR that, had it occurred in a more severe form, might have caused death.
3. Inpatient hospitalization or prolongation of existing hospitalization.

4. Persistent or significant incapacity or substantial disruption of the ability to conduct normal life functions.
5. Congenital anomaly or birth defect.
6. Important medical events that may not result in death, be life threatening, or require hospitalization may be considered serious when, based upon appropriate medical judgment, they may jeopardize the subject and may require medical or surgical intervention to prevent one of the outcomes listed above.

Elective hospitalizations or hospital admissions for the purpose of conduct of protocol mandated procedures are not to be reported as an SAE unless hospitalization is prolonged due to complications.

14.2.4. Other Significant Adverse Events

The events below should be reported (entered on the AE/SAE form) within 24 hours of awareness even if the event does not meet serious criteria:

- Biopsy proven or clinical (Treated) AR
- Chronic rejection
- Infusion Reactions (CTCAE grade 2 or higher)
- Malignancy, PTLD
- Infections (study defined grade 3 or higher)
- COVID-19 infections of any grade

If no other serious criteria are met for COVID-19 infection, the event should be considered of medical importance.

14.3. Grading and Attribution of Adverse Events

14.3.1. Grading Criteria

The study site will grade the severity of adverse events experienced by the study subjects according to the criteria set forth in the National Cancer Institute's Common Terminology Criteria for Adverse Events (CTCAE) *version 4.0*.

This document (referred to herein as the NCI-CTCAE manual) provides a common language to describe levels of severity, to analyze and interpret data, and to articulate the clinical significance of all adverse events. The NCI-CTCAE has been reviewed by the principal investigator and protocol chair and has been deemed appropriate for the subject population to be studied in this protocol.

Infections will be graded using the study-specific scale as described below:

Grade 1 = asymptomatic; clinical or diagnostic observation only; intervention with oral antibiotic, antifungal, or antiviral agent only; no invasive intervention required

Grade 2 = symptomatic; intervention with intravenous antibiotic, antifungal, or antiviral agent; invasive intervention may be required

Grade 3 = any infection associated with hemodynamic compromise requiring pressors; any infection necessitating ICU level of care; any infection necessitating operative intervention; any infection involving the central nervous system; any infection with a positive fungal blood culture; any proven or probable aspergillus infection; any tissue invasive fungal infection; any pneumocystis jiroveci infection

Grade 4 = life-threatening infection

Grade 5 = death resulting from infection

All other adverse events will be graded on a scale from 1 to 5 according to the following standards in the NCI-CTCAE manual:

Grade 1 = mild adverse event.

Grade 2 = moderate adverse event.

Grade 3 = severe and undesirable adverse event.

Grade 4 = life-threatening or disabling adverse event.

Grade 5 = death.

Infection events grade 2 or higher; and all other events CTCAE grade 2 or higher will be recorded on the appropriate AE eCRF for this study.

For grading an abnormal value or result of a clinical or laboratory evaluation (including, but not limited to, a radiograph, an ultrasound, an electrocardiogram etc.), a treatment-emergent adverse event is defined as an increase in grade from baseline or from the last post-baseline value that doesn't meet grading criteria. Changes in grade from screening to baseline will also be recorded as adverse events but are not treatment-emergent. If a specific event or result from a given clinical or laboratory evaluation is not included in the NCI-CTCAE manual, then an abnormal result would be considered an adverse event if changes in therapy or monitoring are implemented as a result of the event/result.

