3.3. Secondary Safety Endpoints

3.3.1. Secondary Safety Endpoints

The safety of PolyTregs (Group 2) will be described in comparison with CNI-based maintenance IS therapy (Group 1) by:

1. Timing, incidence, and severity of polyTregs infusion reaction
2. Timing, incidence, and severity of culture-proven and clinically diagnosed infection after PolyTreg infusion
3. Timing, incidence, and severity of acute rejection using Banff grading
4. Timing and incidence of BK viremia and CMV reactivation
5. Timing and incidence of > 10% decrease in eGFR compared to baseline

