9.1.1. Potential Risks of Treg Administration

T cell suppression

Tregs are known to suppress naïve T cell responses to a variety of antigens. Less is known about ongoing immune responses especially to viruses and bacteria. It is not known whether Tregs will alter protective immunity. Only recipients with current immunizations including TdAP, pneumococcal and seasonal influenza vaccines will be enrolled in the study. During the flu season, seasonal influenza vaccine will be administered prior to the qualifying biopsy for all transplant recipients and at least 28 days prior to Treg isolation. Subjects immune to hepatitis B can be enrolled in the study; or if non-immune/ HBV naïve, can be enrolled only if their kidney donor has negative HB core antibody and negative HB surface antigen.

Infusion reaction

Side effects reported from previous human trials involving T cell infusions include transient fever, chills, and/or nausea. Subjects will be pre-medicated with acetaminophen 650 mg by mouth and diphenhydramine hydrochloride 25-50 mg by mouth or IV, prior to the infusion of Tregs. These medications may be repeated every six hours as needed. Patients will not receive systemic corticosteroids such as hydrocortisone, prednisone, prednisolone (Solu-Medrol) or dexamethasone (Decadron) at any time, except in the case of a life-threatening emergency, since this may have an adverse effect on T cells. If corticosteroids are required for an acute infusion reaction, an initial dose of hydrocortisone 100 mg may be used.

Infection

As with any therapy that suppresses the immune system, there is a risk of developing infections. It should be noted that on a theoretical basis, this risk is minimal, since the total input of Tregs is approximately 3-5% of the endogenous resident Treg population. We will perform plasma CMV DNA quantitative PCR in all recipients prior to enrollment and exclude those who are positive. Study subjects will be monitored for CMV reactivation by plasma CMV DNA quantitative PCR.

Lymphoproliferative disease

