15.3.2. Endpoint Assessments

15.3.2.1 Primary and Secondary Safety Endpoints

Table 7. Analyses of Safety Endpoints describes the safety endpoints and their corresponding parameters to be estimated in the study. Safety endpoints will be listed or summarized, as appropriate, using standard descriptive statistics for continuous and categorical data.

Table 7. Analyses of Safety Endpoints

ENDPOINT	DESCRIPTIVE PARAMETER	ANALYSIS POPULATION
Primary Endpoint		
Incidence of severe acute rejection or antibody mediated rejection in subjects receiving polyTregs in comparison with CNI-based maintenance IS therapy.	Proportion with exact binomial 95% confidence limits	miITT1
Incidence of severe infection in subjects receiving polyTregs in comparison with CNI-based maintenance IS therapy.	Proportion with exact binomial 95% confidence limits	miITT1
Secondary Endpoints – Treg safety		
Incidence of polyTregs infusion reactions (episodes of fever, bronchospasm, hypoxia, cytokine release syndrome, or infusion site reaction)	Proportion with exact binomial 95% confidence limits	miITT2
Severity of polyTregs infusion reactions	Descriptive CTCAE categories	miITT2
Incidence of culture-proven and clinically diagnosed infections	Proportion with exact binomial 95% confidence limits	miITT1
Severity of culture-proven and clinically diagnosed infections	Descriptive CTCAE categories	miITT2
Incidence of severe infection in subjects receiving polyTregs in comparison with CNI-based maintenance IS therapy.	Proportion with exact binomial 95% confidence limits	miITT1
Timing of acute rejection	Mean time to rejection and standard deviation	miITT1
Incidence of acute rejection	Proportion with exact binomial 95% confidence limits	miITT1
Severity of acute rejection	Descriptive Banff criteria	miITT1
Incidence of CMV reactivation	Proportion with exact binomial 95% confidence limits	miITT1
Incidence of BK viremia	Proportion with exact binomial 95% confidence limits	miITT1
Incidence of >10% decrease in eGFR from baseline	Proportion with exact binomial 95% confidence limits	miITT1
Secondary Endpoints – mTOR therapy		
Incidence of acute rejection	Proportion with exact binomial 95% confidence limits	miITT2 (Treg mTOR vs Treg no mTOR)

15.3.2.2 *Supportive Analyses of the Primary Safety Endpoints*

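### The adverse event form starts at grade 2, but two secondary safety endpoints (infusion reactions and infections) are defined with no grade floor

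*Protocol*

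**What the plan says.** **Recording rule.** Protocol 14.3.1 grades infections on a study-specific scale and everything else by CTCAE, then limits what is entered: "Infection events grade 2 or higher; and all other events CTCAE grade 2 or higher will be recorded on the appropriate AE eCRF". Infusion reactions fall under the second part of that rule.

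**Lowest infection grade.** The study scale reads: "Grade 1 = asymptomatic; clinical or diagnostic observation only; intervention with oral antibiotic, antifungal, or antiviral agent only; no invasive intervention required". Grade 2 is described as symptomatic, with intravenous treatment.

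**Exceptions and a competing instruction.** Protocol 14.2.4 lists "COVID-19 infections of any grade" among the events to be entered within 24 hours. For infusion reactions, the same list starts at CTCAE grade 2. Section 14.5.1 requires every serious adverse event, with no grade condition. Section 14.4.3 tells the investigator to record adverse events as described in 14.2, and the definition in 14.2.1 has no grade floor.

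**Endpoints.** Protocol 3.3.1 lists "Timing, incidence, and severity of polyTregs infusion reaction" and "Timing, incidence, and severity of culture-proven and clinically diagnosed infection after PolyTreg infusion". Table 7 (15.3.2.1) spells out the first as "Incidence of polyTregs infusion reactions (episodes of fever, bronchospasm, hypoxia, cytokine release syndrome, or infusion site reaction"). It gives infections of any severity one row and severe infection another. SAP 8.2.1 takes incidence, timing and severity of both, again with no floor. SAP 8.1.1 describes infection severity as running from 1 to 5. SAP section 10, which lists changes from the protocol, adds no grade restriction.

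**The concern.** An endpoint can count only what is collected. The two endpoints are written as any-grade endpoints, but the collection rule supplies grade 2 and above plus two exceptions. Neither document describes another source for a grade 1 infusion reaction or a grade 1 infection. SAP 9.3 describes adverse event data as eCRF entries.

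Three things are at stake.

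- **Incidence.** The reported proportion would be read as any-grade incidence when it is close to incidence at grade 2 or higher.
- **Severity.** The lowest category would be empty or nearly so because of the collection rule, and a reader could take that for a finding.
- **Consistency between sites.** A site following 14.4.3 and a site following 14.3.1 would supply different data for the same events. Sites are not blinded (Protocol 15.2), and the SAP compares infection incidence between groups. Inconsistent application could therefore affect the comparison as well as the level.

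Describing overall safety, infusion reactions included, is part of the primary safety objective (Protocol 1.2). In a small phase I/II cell-therapy trial, readers will look at these tables.

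**Working it through.** The plan states no expected incidence for either endpoint, so there is no figure to reproduce. The check sets the texts side by side, followed by arithmetic on what one missing participant does.

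**Step 1. Compare floor and endpoint.**

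| Item | Grade range | Where |
|---|---|---|
| Adverse event eCRF, infections | 2 and above (study scale) | Protocol 14.3.1 |
| Adverse event eCRF, other events | 2 and above (CTCAE) | Protocol 14.3.1 |
| COVID-19 | any | Protocol 14.2.4 |
| Serious adverse events | any | Protocol 14.5.1 |
| Adverse events generally | no floor | Protocol 14.4.3 with 14.2.1 |
| Infusion reaction endpoint | no floor | Protocol 3.3.1, Table 7; SAP 8.2.1 |
| Infection endpoint | no floor; severity 1 to 5 | Protocol 3.3.1, Table 7; SAP 8.1.1, 8.2.1 |
| Primary infection endpoint | 3 and above | Protocol 3.2 |

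Under 14.3.1 the data for the two secondary endpoints are grade 2 and above, plus COVID-19 and serious events. Under 14.4.3 they would be complete.

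**Step 2. Can a qualifying infection fall below the floor?** Yes. Grade 1 includes infections treated with oral agents only, so an infection that is both culture-proven and clinically diagnosed can be grade 1. A symptomatic one treated by mouth matches grade 2 on symptoms and grade 1 on treatment. The site's choice between them decides whether the event is entered.

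**Step 3. Effect of one participant.** The planned group size is n = 7 (Protocol synopsis, Accrual Objective). A participant whose worst event is an unrecorded grade 1 lowers the proportion by 1/n = 1/7 = 14.3 percentage points. Exact 95% limits (Clopper-Pearson) for x of 7 are the 0.025 quantile of Beta(x, 8 − x) and the 0.975 quantile of Beta(x + 1, 7 − x):

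| x of 7 | Proportion | Exact 95% CI |
|---|---|---|
| 0 | 0% | 0 to 41.0% |
| 1 | 14.3% | 0.4 to 57.9% |
| 2 | 28.6% | 3.7 to 71.0% |
| 3 | 42.9% | 9.9 to 81.6% |

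**Step 4. Range under assumptions.** Let p be the any-grade incidence and g the share of affected participants whose events are grade 1 only. Both are assumed; the documents give neither. Recorded incidence is r = p(1 − g).

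| p | g = 25% | g = 50% | g = 75% |
|---|---|---|---|
| 20% | 15% | 10% | 5% |
| 40% | 30% | 20% | 10% |
| 60% | 45% | 30% | 15% |

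For p = 40% and g = 50%, r = 0.40 × 0.50 = 20%. The chance of seeing no affected participant among 7 rises from 0.60^7 = 2.8% to 0.80^7 = 21.0%.

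**Step 5. Severity.** SAP 8.2.1 restricts the infection severity table to participants with a qualifying infection. An unrecorded grade 1 case therefore drops out of both numerator and denominator. Incidence goes down, while the severity mix among recorded cases moves up.

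**The case against.** The strongest case on the other side has five parts.

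**Grade 1 events are not shut out altogether.** This stands. COVID-19 of any grade and all serious events are entered, and 14.4.3 carries no floor. A reader might infer that grade 1 events are never recorded. The documents support only that 14.3.1 excludes most of them and conflicts with 14.4.3. Nor does the COVID-19 line contradict the floor: a general rule with a named exception is coherent.

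**Orally treated infections may be recorded after all.** This stands in part. Grade 2 is labelled symptomatic, so a site may place such a case there. It would be too strong to say that every infection treated by mouth is lost. The endpoint also requires infection to be culture-proven *and* clinically diagnosed, so some asymptomatic grade 1 findings may not qualify anyway. What remains is an unclear boundary at the recording threshold.

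**Other data may exist.** The case report forms are not among the documents. Vital signs are taken around the infusion, with at least 24 hours of observation (Protocol 5.3). Concomitant medications are collected throughout, and CMV and BK have their own endpoints and scheduled PCR tests. This is fair, but neither document says that the two endpoints draw grade 1 events from any of these.

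**The size is unknown.** This stands. The protocol says "Side effects reported from previous human trials involving T cell infusions include transient fever, chills, and/or nausea" but gives no grades, so a reader should not infer that the floor removes the expected reactions.

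**The consequence is limited.** This also stands. The primary infection endpoint starts at grade 3, participant withdrawal for an infusion reaction at grade 3 (13.1), and the study stopping rules for infusion reactions and infections at grade 4 (13.3). All lie above the floor. The infection floor applies to both groups, and the floor itself is openly stated.

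**Conclusion.** The point holds as a mismatch between what is collected and what two secondary safety endpoints claim to measure. It also holds as a conflict between Protocol 14.3.1 and 14.4.3.

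If 14.3.1 is followed, any-grade incidence of infusion reactions and of qualifying infections is understated whenever grade 1 events occur. The shortfall is 14.3 percentage points per affected participant in a group of 7. The total cannot be derived, and the tables above are illustrations. A reader might infer that tolerability will be overstated by a known amount; the documents do not support that.

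The conclusion rests on three assumptions: sites apply 14.3.1 rather than 14.4.3, no other form feeds grade 1 events into these endpoints, and some participants have grade 1 as their worst event. The primary safety endpoints and the infection and infusion-reaction stopping thresholds are unaffected.

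**What to change.** 1. Reconcile Protocol 14.3.1 with 14.4.3 so that one recording rule applies, with the COVID-19 and serious-event exceptions stated beside it.
2. If data collection is still open, state that all infusion reactions and all culture-proven and clinically diagnosed infections are recorded regardless of grade. Keep *and*, so that the endpoint is not widened by accident. Word infection grades 1 and 2 so that a symptomatic, orally treated infection has a single grade.
3. If data are closed, label both endpoints as grade 2 or higher in Protocol 3.3.1, Table 7 and SAP 8.2.1. Note that COVID-19 of any grade and serious events are also included, and list the relabelling in SAP section 10.

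The second step costs a few more eCRF entries in 14 participants. The third needs no new data; its price is a narrower endpoint.

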14.3.2. Attribution Definitions

The relationship, or attribution, of an adverse event to the study therapy regimen or study procedure(s) will initially be determined by the site investigator and recorded on the appropriate AE/SAE eCRF. Final determination of attribution for safety reporting will be determined by DAIT/NIAID. The relationship of an adverse event to study therapy regimen or procedures will be determined using the descriptors and definitions provided in Table 6.

For additional information and a printable version of the NCI-CTCAE manual, consult the NCI-CTCAE web site:
<http://ctep.cancer.gov/reporting/ctc.html>.

Table 6. Attribution of Adverse Events

Code	Descriptor	Relationship (to primary investigational product and/or other concurrent mandated study therapy or study procedure)
Unrelated Category		
1	Unrelated	The adverse event is clearly not related: there is insufficient evidence to suggest a causal relationship.
Related Categories		
2	Possible	The adverse event has a reasonable possibility to be related; there is evidence to suggest a causal relationship.
3	Related	The adverse event is clearly related.

Attribution of adverse event to tacrolimus, MMF/MPA, and prednisone will not be assessed in this study because these medications are used as standard of care for kidney transplant recipients.

Attribution assessment for the following study interventions and procedures will be made when a SAE is reported:

Study therapy regimen:

1. polyTregs

Study mandated procedures:

1. Leukapheresis
2. Kidney biopsy
3. Blood Draw (Donor or Recipient)
4. IS regimen conversion / Everolimus

14.4. Collection and Recording of Adverse Events**14.4.1. Collection Period**

Adverse events will be collected from the time of first study mandated procedure until a subject completes study participation or until 30 days after he/she prematurely withdraws (without withdrawing consent) or is withdrawn from the study.

Note that the study eligibility is performed as a standard of care surveillance biopsy with no collection of research specimens. The eligibility biopsy is not considered a study mandated procedure for these reasons.

14.4.2. Collecting Adverse Events

Adverse events (including SAEs) may be discovered through any of these methods:

- Observing the subject.
- Interviewing the subject [e.g., using a checklist, structured questioning, diary, etc.] .
- Receiving an unsolicited complaint from the subject.
- In addition, an abnormal value or result from a clinical or laboratory evaluation can also indicate an adverse event, as defined in Section 14.2.4, *Grading and Attribution of Adverse Events*.

